58 Randomization schedules will be separate for Cohort A and Cohort B and will be stratified by
59 site. Cohort A will be participating in a factorial design arm. Eligible participants will be
60 randomly assigned (1:1:1:1) to one of 4 groups:

61 • HCL and placebo
62 • HCL and verapamil
63 • non-HCL and placebo
64 • non-HCL and verapamil.

65

66 Cohort B will be not be assigned to verapamil due to their lower body weight. These participants
67 will be randomly assigned 2:1 to either HCL or non-HCL.

68

69 Participants assigned to HCL will receive intensive diabetes management with frequent contacts
70 by study staff with the goal of near-normalization of glucose concentrations. Participants
71 assigned to non-HCL will receive a Dexcom G6 CGM and diabetes management will follow
72 usual care.

73

74 Participants will be followed for 12 months from diagnosis, with visits timed from diagnosis at 6,
75 13, 26, 39, and 52 weeks. Participants will have a mixed meal tolerance test (MMTT) performed,
76 HbA1c measured, insulin dose (units/kg/day) recorded, CGM data uploaded, and pregnancy
77 testing performed (if indicated) at some or all of the previously noted timepoints.

78

79 Additional Procedures for Cohort A

80 Drug will be double blinded. Cohort A will have additional safety visits 1 week after initiation
81 of study drug and after each study drug dose increase.

82

83

84 **2. Consistency of Statistical Analysis Plan with Protocol**

85 Prior to the start of the study, the following secondary outcomes have been added that were not
86 specified in the protocol:

87 • Percentage of participants with peak C-peptide ≥ 0.2 pmol/ml
88 • Percentage of time sensor glucose from 70 to 140 mg/dL
89 • Percentage of participants with $\geq 70\%$ of sensor glucose values from 70 to 180 mg/dL
90 • Percentage of time sensor glucose > 140 mg/dL
91 • Total daily insulin per kg
92 • Basal: Bolus ratio

93
94 Serious adverse events has been added as a safety outcome in place of hospitalizations.

95 Otherwise, the author of this SAP has verified that the analyses described in this document are
96 consistent with the version of the protocol listed in the version history table above.

97
98 **3. Primary Statistical Hypotheses**

99 The primary outcome is the C-peptide area under the curve (AUC) in response to a 2-hour MMTT
100 at 52 weeks.

101
102 **3.1 HCL vs. non-HCL**

103 • *Null Hypothesis:* There is no difference in the C-peptide AUC in response to a 2-hour

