104 MMTT at 52 weeks between HCL with intensive care and non-HCL with standard care
105 for the combined Cohort A and B population.
106 • *Alternative Hypothesis:* There is a nonzero difference in the C-peptide AUC in response
107 to a 2-hour MMTT at 52 weeks between HCL with intensive care and non-HCL with
108 standard care for the combined Cohort A and Cohort B population.

109
110 **3.2 Verapamil vs. Placebo**

111 • *Null Hypothesis:* There is no difference in the C-peptide AUC in response to a 2-hour
112 MMTT at 52 weeks between verapamil and placebo for the Cohort A population.
113 • *Alternative Hypothesis:* There is a nonzero difference in the C-peptide AUC in response
114 to a 2-hour MMTT at 52 weeks between verapamil and placebo for the Cohort A
115 population.

116
117 **4. Sample size**

118 The sample size calculation is detailed in a separate document and is summarized below. Sample
119 size was driven by the verapamil vs. placebo comparison as the test only includes participants in
120 Cohort A. The mean of the transformed C-peptide ($\log(AUC + 1)$) and the root mean square
121 error in the placebo group were assumed to be 0.315 and 0.18, respectively, based on 90% CIs
122 from prior studies (1). The corresponding geometric-like mean C-peptide value of 0.370
123 pmol/mL was calculated using the inverse transformation: $\exp(0.315) - 1$. A recent randomized
124 trial (2) found a 62% increase in mean C-peptide in verapamil compared with placebo, although

125 the total sample size was small (N=24) and confidence intervals were wide. Therefore, this
126 study assumed a smaller, 50% increase in mean C-peptide using verapamil. The expected
127 geometric-like mean C-peptide value in the verapamil arm was $0.370 \cdot 1.50 = 0.555$ pmol/mL.
128 After a $\log(x+1)$ transformation, the mean values in the control and treatment groups are 0.315
129 and 0.441, respectively, giving a treatment effect of $0.441 - 0.315 = 0.126$.

130 With these estimates, a sample size of 88 participants in Cohort A was calculated to provide 90%
131 power with a 5% two-sided type 1 error rate and a 1:1 treatment group allocation to detect a
132 verapamil vs. placebo treatment group difference assuming the true relative difference between
133 groups was 50%. To account for a 10% dropout rate, the sample size in Cohort A will be 98
134 participants.

135 A sample size of 33 participants for Cohort B was selected based on convenience. Participants

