136 in Cohort B will be allocated to either HCL or non-HCL in a 2:1 treatment group allocation.
137 Thus, 131 participants are expected to be enrolled in either Cohort A or Cohort B with
138 approximately 71 participants in HCL/intensive care and 60 participants in non-HCL/standard
139 care arm. Assuming around a 10% dropout rate, an HCL/intensive care treatment effect of 50%,
140 and an upper confidence limit estimate of 0.18 for the standard deviation (same presumed
141 estimates for verapamil vs. placebo comparison), this study has 96% power to detect a significant
142 HCL/intensive care vs. non-HCL/standard care treatment group difference with a type 1 error
143 rate of 5%.

144

145 **5. Outcome Measures**

146 Primary Efficacy Outcome

147 The primary outcome is the C-peptide in response to a 2-hour MMTT at 52 weeks. This is
148 measured as the area under the stimulated C-peptide curve (AUC).

149

150 Secondary Efficacy Outcomes

151 *C-peptide*

- 152 • C-peptide AUC at 13, 26, and 39 weeks (52 weeks is primary outcome)
- 153 • Peak C-peptide during a 2-hour MMTT at 13, 26, 39, and 52 weeks
- 154 • Percentage of patients with peak C-peptide ≥ 0.2 pmol/ml at 13, 26, 39, and 52 weeks

155

156 *CGM Metrics*

157 The following CGM-derived indices will be computed over the study period for 24 hours,
158 daytime (6:00am to 11:59pm) and nighttime (midnight to 5:59am) at 6, 13, 26, 39, and 52 weeks:

- 159 • Mean glucose
- 160 • Percentage of time sensor glucose from 70 to 180 mg/dL
- 161 • Percentage of time sensor glucose from 70 to 140 mg/dL
- 162 • Percentage of patients with $\geq 70\%$ of sensor glucose values from 70 to 180 mg/dL
- 163 • Percentage of time sensor glucose > 140 mg/dL
- 164 • Percentage of time sensor glucose > 180 and > 250 mg/dL

165 • Percentage of time sensor glucose <54 and <70 mg/dL
166 • Coefficient of variation

167
168 *HbA1c*

169 Values at 13, 26, 39, and 52 weeks will include the following:

170 • Mean HbA1c
171 • Percentage of patients with an HbA1c <7.0% and <6.5%

172
173 *Insulin*

174 Values at 6, 13, 26, 39, and 52 weeks

175 • Total daily insulin per kg
176 • Basal: Bolus ratio

177
178 **5.1 C-Peptide**

179 *Area Under the Curve (AUC)*

180 The stimulated C-peptide AUC will be calculated for an MMTT if the following conditions hold:

181 • A C-peptide measurement available at 0 minutes.
182 • At least three C-peptide measurements available among the following 5 times: 15

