221 52 weeks). A minimum of 5 days (120 hours) of CGM data will be required to calculate CGM
222 indices at each visit.

223
224 For daytime (6:00am to 11:59pm) versions of the CGM metrics, at least 80 hours of data will be
225 required; and for the nighttime versions (midnight to 5:59am), at least 40 hours of data will be
226 required.

227
228 **6. Primary Analyses**

229 Primary analyses will follow the intent to treat principle. Primary outcome is C-peptide AUC at
230 the 52-week visit. The protocol window is 52-weeks from diagnosis \pm 14 days, but out-of-
231 window MMTT results will be included in the analysis if obtained within 52 weeks from
232 diagnosis \pm 42 days (Day 322-406 from the date of diagnosis). Any MMTT results outside this
233 analysis window will be excluded from the primary analysis and treated as missing data.

234

235 **6.1 HCL vs. non-HCL**

236 The HCL/intensive care versus non-HCL/standard care comparison will combine participants from
237 Cohort A and B. Comparisons for HCL versus non-HCL will be pooled over verapamil groups
238 (verapamil, placebo, neither [Cohort B]). Summary statistics appropriate to the distribution, mean
239 (SD) or median (quartiles) of log(AUC+1), will be tabulated for each treatment group at 52 weeks.
240 Boxplots, with HCL vs Non-HCL groups next to each other, will be produced for each visit.

241

242 A constrained longitudinal regression model will be constructed with log(AUC+1) as the
243 dependent variable controlling for age, time from diagnosis to randomization, verapamil group
244 (verapamil, placebo, or neither [Cohort B]), and clinical site (random effect). C-peptide values at
245 baseline, 13, 26, 39 and 52 weeks will be included in the longitudinal model which will account
246 for the correlated data from the same participant using an unstructured covariance matrix. If there
247 are convergence issues, a simpler covariance structure (e.g., autoregressive or compound

248 symmetry structure) will be used. The model specified above is equivalent to adjusting for baseline
249 as a covariate, but also has the advantage of being able to handle any cases of missing baseline.

250
251 A time by treatment (HCL) interaction will be included in the model so that different treatment
252 effects can be estimated. The treatment effect at 52 weeks from this model (point estimate, 95%
253 confidence interval (CI), and p-value) will be reported as the primary analysis results.

254

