295 analysis is \geq 95% of the N in the primary intent-to-treat analysis.

296

297 **8. Secondary Analyses**

298 As described above for the primary analysis, comparisons of HCL versus non-HCL will include
299 cohorts A and B and will be pooled over verapamil groups. Comparisons of verapamil versus
300 placebo will be limited to Cohort A and will be pooled over HCL and usual care groups.

301

302 Descriptive summary statistics appropriate to the distribution will be given for each secondary
303 efficacy outcome listed above in Section 5 by treatment group at each visit. Corresponding
304 boxplot figures of baseline and 52 weeks, boxplot figures over time, scatterplots of baseline
305 versus 52 weeks, and histograms of baseline, 26 weeks, and 52 weeks will be constructed for
306 selected metrics.

307

308 **8.1 Formal Statistical Comparisons of Treatment Groups**

309

310 C-peptide Related Secondary Efficacy Outcome

311 Formal statistical comparisons of treatment groups will limited to C-peptide AUC at 13, 26, and
312 39 weeks (52 weeks is the primary analysis described above).

313

314 Other Secondary Efficacy Outcomes

315 Formal statistical comparisons of treatment groups for other secondary efficacy outcomes will be
316 limited to the following at 26 and 52 weeks:

317 • Mean HbA1c
318 • Total daily insulin per kg
319 • Selected overall (24 hours) CGM indices:

320 ➤ Mean glucose
321 ➤ Percentage of time sensor glucose from 70 to 140 mg/dL
322 ➤ Percentage of time sensor glucose from 70 to 180 mg/dL
323 ➤ Percentage of time sensor glucose >180 mg/dL
324 ➤ Percentage of time sensor glucose >250 mg/dL
325 ➤ Percentage of time sensor glucose <54 mg/dL
326 ➤ Percentage of time sensor glucose <70 mg/dL

327

328 Separate comparisons for HCL versus non-HCL and verapamil versus placebo will be done
329 similarly as described above for the primary analysis. Except where noted otherwise below in
330 Sections 8.3 and 8.5, the general approach for analysis of secondary outcomes will be as follows:
331 For each outcome, a constrained longitudinal model will be fit adjusting for age, time from
332 diagnosis to randomization, verapamil group (for HCL analysis), HCL group (for verapamil

333 analysis) and clinical site as a random effect. A treatment by time interaction will be included in
334 the model and treatment effects (and 95% CI) will be reported separately at 26 and 52 weeks.

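### SAP 6.1 names a by-visit term only for HCL; if verapamil group is fitted as constant over visits, the week-52 HCL estimate is biased when the Cohort A average and Cohort B separate after baseline

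*SAP*

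**What the plan says.** SAP 6.1 specifies a constrained longitudinal model for log(AUC+1) at baseline and weeks 13, 26, 39 and 52, with an unstructured covariance. The transformed AUC is the "dependent variable controlling for age, time from diagnosis to randomization, verapamil group" and clinical site (random). Verapamil group has three levels: verapamil, placebo, and neither for Cohort B.

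One interaction is named: "A time by treatment (HCL) interaction will be included in the model so that different treatment" effects can be estimated. Nothing says whether the other covariates have constant or visit-specific effects. The same section adds: "The model specified above is equivalent to adjusting for baseline" as a covariate.

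SAP 8.1 uses the same construction for secondary outcomes ("A treatment by time interaction will be included in" the model). SAP 8.3 takes the week 13, 26 and 39 AUC comparisons from the primary model. SAP 8.5 makes the CGM models unconstrained, because there is no baseline CGM value.

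On design, SAP 1 states: "Cohort B will be not be assigned to verapamil due to their lower body weight". Cohort A is randomised 1:1:1:1. Under SAP 4, participants "in Cohort B will be allocated to either HCL or non-HCL in a 2:1 treatment group allocation".

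**The concern.** Because baseline is part of the outcome, a covariate without a visit term has one effect shared by all five visits. For verapamil group, this forces the drug effect at week 52 to equal the difference at baseline, before any drug was taken. It also forces the gap between Cohort B and placebo to stay fixed for a year. Adjusting for baseline as a covariate imposes neither restriction. The two statements in SAP 6.1 therefore describe different models, and a programmer could follow either one.

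The choice matters for HCL because of Cohort B. In Cohort A, HCL is balanced over drug. Cohort B receives no drug and is weighted towards HCL. If Cohort A, averaged over drug, moves away from Cohort B after baseline and the model cannot represent that, part of the movement is credited to or taken from HCL. A working verapamil arm would by itself raise the Cohort A average. The affected quantity is one of the two primary results.

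**Working it through.** **Inputs from the documents.** Planned effect 0.126 on log(AUC+1), for verapamil and also for HCL (SAP 4: "study assumed a smaller, 50% increase in mean C-peptide using verapamil", with the same 50% for HCL). SD 0.18. HCL 71 and non-HCL 60, with 10% dropout. Cohort A 98 (four cells of 24.5). Cohort B 33 (22 HCL, 11 non-HCL).

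**Assumptions, not in the documents.** Within-participant correlation 0.3-0.95, either autoregressive (adjacent visits) or compound symmetry. Effects that rise linearly to week 52 (ramp) or are complete at week 13 (step). Cohort B follows placebo, except where stated. 0.18 is read as the baseline-adjusted SD.

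**1. The plan's own power.** With 71 x 0.9 = 63.9 and 60 x 0.9 = 54, SE = 0.18 x sqrt(1/63.9 + 1/54) = 0.0333. Then 0.126/0.0333 - 1.96 = 1.83, so power is about 96.6% (96.4% with the noncentral t). The stated 96% is reproduced.

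**2. Imbalance and ceiling.** Cohort B is 22/71 = 31.0% of HCL and 11/60 = 18.3% of non-HCL, a difference of 0.127. Let D be the gap opened by week 52 between the Cohort A average and Cohort B: D = half the verapamil effect + any extra Cohort B decline. With verapamil as planned and Cohort B following placebo, D = 0.126/2 = 0.063. If the model absorbed none of this gap, the shift would be 0.1265 x 0.063 = 0.0080, or 6.3% of 0.126.

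**3. Large-sample maximum likelihood fit.** The five-visit model was fitted to the expected cell means (cell sizes x 0.9), with the unstructured covariance iterated to its limit. Age, time from diagnosis and site were left out. The true HCL effect is 0.126 and the verapamil effect is as planned.

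| Correlation | Effect shape | Literal model | % low | Literal SE | Power |
|---|---|---|---|---|---|
| AR 0.3 | step | 0.1241 | 1.5 | 0.0335 | 96% |
| AR 0.3 | ramp | 0.1221 | 3.1 | 0.0339 | 95% |
| AR 0.70 | ramp | 0.1211 | 3.9 | 0.0341 | 94% |
| AR 0.85 | ramp | 0.1200 | 4.7 | 0.0344 | 94% |
| AR 0.95 | ramp | 0.1188 | 5.7 | 0.0348 | 93% |
| CS 0.5 | step | 0.1214 | 3.6 | 0.0340 | 95% |
| CS 0.95 | ramp | 0.1182 | 6.2 | 0.0350 | 92% |

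With verapamil-group-by-visit terms, every row returns 0.1260, SE 0.0336 and power 96.3%. The largest shift is 0.126 - 0.1182 = 0.0078, and 0.0078/0.0336 = 0.23 SE.

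**4. Source of the power loss.** In the last row, the shift alone gives 0.1182/0.0336 - 1.96 = 1.56, or 94%. The literal model's larger SE, 0.0350, brings it to 92%. The extra SE arises because unmodelled verapamil variation stays in the residual.

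**5. Where the bias vanishes, grows or reverses.**
- No divergence, or only a constant Cohort B offset: exactly zero.
- Verapamil effect 0.126 but Cohort B at the Cohort A average (declining 0.063 less than placebo, same shape over visits): zero.
- Cohort A alone, or Cohort B allocated 1:1: zero.
- Planned verapamil effect plus an assumed extra Cohort B decline of 0.05 (AR 0.70-0.95, ramp): 0.1174-0.1132, 7-10% low. With 0.10: 0.1138-0.1076, 10-15% low.
- No verapamil effect and Cohort B declining 0.10 less (assumed): 0.1338-0.1374, 6-9% high.

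**6. Simulation.** 1,500 replicates with 131 randomised, 10% dropout, correlation 0.85, and age and time from diagnosis as constant covariates. The literal model differed from the by-visit model by -0.0046 (3.7% of 0.126) with the planned verapamil effect, and by 0.0000 with no divergence. With no HCL effect and the planned verapamil effect, type I error was 5.2-5.5%.

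**The case against.** The strongest reply is that the literal model is only one reading. SAP 6.1 says that an HCL-by-time term will be included. It does not say that other effects are held constant, and its equivalence sentence points to the by-visit model. That stands: the fault is an inconsistent specification, and the text does not show that the sponsor chose a biased estimator.

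The size is also modest. On planned effects the shift is under a quarter of one SE, and type I error is hardly affected. SAP 4 calls 0.18 an "upper confidence limit estimate of 0.18 for the standard deviation", so the powers above are conservative. This also stands.

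Three stronger readings are tempting, and the documents do not support them:
- *Any verapamil-placebo divergence contaminates the HCL estimate.* It does not. HCL and drug are balanced in Cohort A, so the split matters only through the gap between the Cohort A average and Cohort B.
- *Cohort B will decline faster, so the larger figures apply.* Protocol 1.1 links faster decline to age under 12, but the cohorts are divided by weight and no cohort-specific slope is given.
- *All secondary outcomes share the problem.* SAP 8.5 exempts the CGM indices. Of the non-C-peptide outcomes formally compared in SAP 8.1, only HbA1c and total daily insulin per kg use the constrained model.

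**Conclusion.** The point holds as a specification conflict in a primary analysis and should be fixed. Under the literal reading, the equivalence claim fails and the week-52 HCL estimate is biased whenever the Cohort A average separates from Cohort B after baseline. With verapamil working as planned and Cohort B following placebo, the estimate is about 1.5-6% low, and power is about 92-96% against 96%. Only the 0.126, the 0.18 and the allocation come from the documents. The correlation, the effect shape and the Cohort B course are assumed, so a narrower range should not be quoted as the plan's own.

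The bias does not shrink with sample size. The missing-data and covariate-imbalance sensitivity analyses in SAP 10 do not address it. Leaving the model open would also allow the choice to be made after results are seen.

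**What to change.** Add one sentence to SAP 6.1: the three-level verapamil group enters with visit-specific effects, with verapamil and placebo constrained equal at baseline and Cohort B free at every visit. In SAP 8.1, apply the same sentence to HbA1c and total daily insulin per kg, but not to the CGM metrics. The earlier-visit AUC comparisons in SAP 8.3 follow automatically. If constant effects were intended, say so and delete the equivalence statement.

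By-visit terms for age and time from diagnosis are optional and not needed to remove this bias. In SAP 6.2, an HCL-by-visit term (equal at baseline) would affect precision only.

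Cost: verapamil group goes from 2 mean parameters to 9 (4 post-baseline verapamil effects plus 5 for Cohort B), so 7 extra. With no divergence the SE is 0.0336 against 0.0333-0.0334, about 1% larger. All 1,500 simulated fits converged in each of five scenarios, but without the site random effect, so convergence of the full model is untested. The simpler-covariance fallback already in SAP 6.1 would apply. No new data are needed. The SAP version history lists follow-up as ongoing at version 2.0, so the change could be made before analysis.
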